8.2.5 ADVERSE EVENT REPORTING

Required reporting must be submitted through the StrokeNet WebDCU™ as described and within the timeframes described in NIH StrokeNet Network Standard Operating Procedure ADM 12 Central Institutional Review Board (cIRB) Reporting https://www.nihstrokenet.org/docs/default-source/strokenet-sops/adm12_cirb_reporting_060314.pdf?sfvrsn=2.

8.2.6 SERIOUS ADVERSE EVENT REPORTING

All SAEs are required to be reported in WebDCU™ within 24 hours of the study site being made aware of the occurrence of the SAE. The investigators are required to provide relevant information such as description of the SAE, date/time of onset and resolution, severity and seriousness, action taken, and suspected relationship to the study intervention. Reporting of SAEs will trigger notification of the event to the Project Manager (PM). After reviewing the SAE for completeness and accuracy, the PM will forward the SAE to the MSM who will conduct an independent review of each SAE to determine its relationship to the study intervention along with other elements. Within 72 hours of receipt of the SAE for review, the IMSM will enter his opinion into WebDCU™ as to whether the SAE is, in fact, serious, unexpected, and related to the study drug. After the submission of the initial SAE Report, the site investigator at the corresponding clinical site will be responsible for obtaining follow-up information about the event and reporting it in WebDCU™.

8.3 UNANTICIPATED PROBLEMS

8.3.1 DEFINITION OF UNANTICIPATED PROBLEMS (UP)

The Office for Human Research Protections (OHRP) considers unanticipated problems involving risks to subjects or others to include, in general, any incident, experience, or outcome that meets all of the following criteria:

- Unexpected in terms of nature, severity, or frequency given (a) the research procedures that are described in the protocol-related documents, such as the Institutional Review Board (IRB)-approved research protocol and informed consent document; and (b) the characteristics of the subject population being studied;

- Related or possibly related to participation in the research (“possibly related” means there is a reasonable possibility that the incident, experience, or outcome may have been caused by the procedures involved in the research); and
- Suggests that the research places subjects or others at a greater risk of harm (including physical, psychological, economic, or social harm) than was previously known or recognized.

This definition could include an unanticipated adverse device effect, any serious adverse effect on health or safety or any life-threatening problem or death caused by, or associated with, a device, if that effect, problem, or death was not previously identified in nature, severity, or degree of incidence in the investigational plan or application (including a supplementary plan or application), or any other unanticipated serious problem associated with a device that relates to the rights, safety, or welfare of subjects (21 CFR 812.3(s)).

8.3.2 UNANTICIPATED PROBLEM REPORTING

The investigator will report unanticipated problems (UPs) to the cIRB. The UP report will include the following information:

- Protocol identifying information: protocol title and site name;
- A detailed description of the event, incident, experience, or outcome;
- An explanation of the basis for determining that the event, incident, experience, or outcome represents a UP;
- A description of any changes to the protocol or other corrective actions that have been taken or are proposed in response to the UP.

To satisfy the requirement for prompt reporting, UPs will be reported using the following timeline:

- UPs that are serious adverse events (SAEs) will be reported to the cIRB within 10 days of the investigator becoming aware of the event.
- Any other UP will be reported to the DCC/study sponsor within 5 days of the investigator becoming aware of the problem.
- All UPs should be reported to appropriate institutional officials (as required by an institution's written reporting procedures), the supporting agency head (or designee), and the Office for Human Research Protections (OHRP) within 1 month of the IRB's receipt of the report of the problem from the investigator.

8.3.3 REPORTING UNANTICIPATED PROBLEMS TO PARTICIPANTS

Unanticipated problems judged after review by the TRANSPORT2 protocol PIs, cIRB, DSMB, or NINDS to require changes to the informed consent, study protocol, or background knowledge and training provided to sites will be communicated to all participating site PIs by the National Coordinating Center (NCC) or NDMC. This will be accomplished by email and may be supplemented by request for confirmation of receipt and follow-up by phone, all with assistance of the relevant Regional Coordinating Center when necessary. Any change in protocol or risk of the research will be communicated by site staff, by phone (supplemented by other means as necessary), to active intervention arm participants or their caretakers/other contacts.

9 STATISTICAL CONSIDERATIONS

9.1 STATISTICAL HYPOTHESES

- Primary Efficacy Endpoint(s):

The primary null hypothesis is that there is no difference in the least-squares mean estimate of the change in FM-UE scale on Day 15 after the initiation of the 14 day intervention among the three dose groups.

$$H_0: \hat{Y}_{sham,15d} = \hat{Y}_{2mA,15d} = \hat{Y}_{4mA,15d}$$

H_A : The means are not all equal

- Secondary Efficacy Endpoint(s):

The secondary null hypothesis is that there is no difference in the least-squares mean estimate of the change in Wolf-Motor Functional Test (WMFT) time score and Stroke Impact Scale (version 3.0, SIS) hand subscale.

9.2 SAMPLE SIZE DETERMINATION

A change of 4.25-7.25 points on the FM-UE scale is considered to be a meaningful clinically important difference (MCID)¹¹⁶. This study is powered under the assumption that mCIMT alone, will at least achieve this intervention effect (4.5) and furthermore intervention with either 2 mA or 4 mA tDCS will further increase the change in FM-UE scale from the baseline by 4.5 points (i.e., a minimum intervention effect of 9.0). Secondly, based on the meta-analysis of previous trials assessing tDCS in stroke patients³⁹, a conservative estimate of the intervention variability is defined as SD = 7. Based on these assumptions, the current study requires 31 subjects per arm to estimate the 90% confidence interval for the treatment effect in each arm with a standard error of ± 1.3 , assuming an ANOVA-type testing approach which is more conservative than the proposed analysis model which includes multiple time points and adjusts for covariates.

This level of precision was determined to be sufficiently informative to plan a Phase III trial. Specifically, the confidence interval for a clinically meaningful treatment effect will exclude the hypothesized null effect size of 4.5; that is, the estimate and 90% confidence interval for a clinically meaningful treatment might be 9.0 (6.9, 11.1). Moreover, the choice of standard error represents a balance between the level of precision in the estimate and the number of subjects/resources expended during this phase of investigation (**Fig. 9, below**). Further, if the estimate of the standard deviation were overly conservative, the precision of the treatment effect estimate would increase. (N.B. Planning estimates of the null treatment effect size, 4.5, do not impact power as long as the MCID from stimulation remains at 4.5 points.)

In addition, with a sample size of 31 subjects per group, a two-sided type I error rate of 10%, and standard deviation of 7, if the true pattern of mean changes is 4.5, 9.0, and 9.0 for the sham, 2 mA, and 4 mA groups respectively, we would have 83% power to reject the null hypothesis. A 10% type I error rate was selected in consideration of the track record for safety in the intervention, the relative cost of committing a type I and type II error with respect to trial duration, subject utilization, and the remaining need for a subsequently planned Phase III trial should the current trial demonstrate promising results. Based on a conservative estimate from the EXCITE and VECTOR trial^{14, 19}, 8% of subjects are expected to complete less than 10 full sessions of tDCS + mCIMT in the specified 14 day time-window. Thus, the sample size is inflated for the cross-over in treatment effect using an inflation factor of $1/(1-0.08)^2$.¹¹⁷ In addition, up to 15% of subjects may be lost to follow-up prior to collection of the primary outcomes at the 3-month follow-up visit.

Therefore, an inflation of 115% is used to account for the missing samples in the ITT primary analysis. As a result, the final estimated sample size is 43 per group (or 129 subjects in total). Finally, considering the longitudinal nature of the design and adjustment for key covariates, the power will be maintained when using an auto-regressive (1) correlation structure regardless of the degree of correlation between FM-UE scale measured on proximal visits or the strength of the covariates as predictors. We elected not to further reduce the sample size both because a robust estimate of these quantities is not currently available, and to retain sufficient power to evaluate secondary hypotheses.

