9.4.2 ANALYSIS OF THE PRIMARY EFFICACY ENDPOINT(S)

The change in FM-UE Scale in each treatment arm will be modeled using generalized linear mixed effects repeated measures model, where the dependent variable is the change from baseline in

FM-UE to post-intervention visit; the model is adjusted for intervention arm, baseline FM-UE, time from stroke, visit and site; and the primary outcome is the fitted estimate at day 15. Model assumptions, including normality, will be assessed and appropriate transformations will be used in keeping with best practices and conventional approaches in the literature. If the primary null hypothesis is rejected, all pairwise secondary hypotheses will be tested using a Dunnett type multiple comparisons correction^{118, 119}.

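### Section 9.2 states precision for one active arm's mean change (SE 1.3) as if it were the treatment effect; active minus sham has SE 1.78 and an unadjusted 90% CI of about 4.5 (1.6, 7.4)

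*Combined protocol and SAP*

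**What the plan says.** Section 9.2 (Sample Size Determination) assumes that mCIMT alone produces a gain of at least 4.5 FM-UE points. It assumes that 2 mA or 4 mA stimulation adds a further 4.5, so that an active arm changes by at least 9.0 in total, with an SD of 7. From this it concludes that the study "requires 31 subjects per arm to estimate the 90% confidence interval for the treatment effect in each arm with a standard error of" 1.3.

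The next paragraph states: "This level of precision was determined to be sufficiently informative to plan a Phase III trial". The reason given is that "the confidence interval for a clinically meaningful treatment effect will exclude the hypothesized null effect size of 4.5", with 9.0 (6.9, 11.1) as the example. A note closes the paragraph: "Planning estimates of the null treatment effect size, 4.5, do not impact power as long as the MCID from stimulation remains at 4.5 points".

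Power comes second, as an additional consideration. With means of 4.5, 9.0 and 9.0, 31 per group and two-sided alpha of 10%, "we would have 83% power to reject the null hypothesis".

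The inferential target is set elsewhere. Section 9.1 makes the primary null the equality of the three arms' mean changes at day 15. Section 9.4.2 adds: "If the primary null hypothesis is rejected, all pairwise secondary hypotheses will be tested using a Dunnett type multiple comparisons correction".

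**The concern.** The interval 9.0 (6.9, 11.1) is for a change from baseline in one arm, which includes everything mCIMT and natural recovery contribute. Section 9.2 calls it a treatment effect and judges it against 4.5 as the null. But 4.5 is the planning value for the sham arm's mean, and the same section presents it as a floor. Sham is a concurrent arm of equal size under 1:1:1 allocation, so its mean carries the same sampling error as an active arm's. Excluding a fixed 4.5 therefore does not isolate an effect of stimulation.

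The note that the 4.5 planning value does not affect power is correct for a comparison between arms. It does not carry over to the one-arm criterion printed just above it, which depends directly on where the sham mean lies.

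What is at stake is how the stated precision is used. A Phase III trial of tDCS would be planned on active minus sham. A reader who takes the printed SE and interval as the precision of that effect will think it better known than it is.

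**Working it through.** **Inputs.** From section 9.2: n = 31 per arm before inflation, SD = 7, sham mean 4.5, active means 9.0, added effect 4.5, two-sided alpha 10%. From section 4.1: 1:1:1 allocation.

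**1. Reproduce the printed figures.** They come out as a one-arm mean.
- SE = SD/√n = 7/√31 = 1.257, printed as 1.3.
- 90% CI = 9.0 ± 1.645 × 1.257 = (6.93, 11.07), printed as (6.9, 11.1). Using t on 30 or 90 df gives the same limits to one decimal.

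**2. Reproduce the power.** A one-way ANOVA with 3 × 31 subjects, SD 7, alpha 0.10 and means 4.5/9/9 gives 82.8% by the noncentral F, matching the stated 83%. This figure includes the sham arm's variance.

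**3. Precision of active minus sham.**
- SE = SD × √(2/n) = 7 × √(2/31) = 1.778, which is √2 = 1.414 times the one-arm SE.
- Unadjusted 90% CI = 4.5 ± 1.645 × 1.778 = 4.5 ± 2.92 = (1.58, 7.42). With t on 90 df it is (1.55, 7.45).
- An SE of 1.3 for the difference would need 2 × (7/1.3)² = 58 evaluable subjects per arm.

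**4. Chance that each interval excludes its null** (noncentral t, 90 df).

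| Criterion | Truth | Probability |
|---|---|---|
| One-arm lower 90% limit above 4.5 | arm mean 9.0 | 0.972 |
| Difference lower 90% limit above 0, unadjusted | difference 4.5 | 0.807 |

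**5. The one-arm criterion when stimulation adds nothing.** If all arms share a common mean, the chance that an active arm's lower limit exceeds 4.5 is as follows. The means of 5, 6 and 7 are assumptions for illustration and are not in the documents.

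| Common mean | 4.5 | 5 | 6 | 7 |
|---|---|---|---|---|
| Probability | 0.050 | 0.106 | 0.322 | 0.629 |

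**6. After multiplicity correction.** Section 9.4.2 can be read as two comparisons with sham (Dunnett) or as all three pairs. Simulation with 2,000,000 replicates and 90 df, at means 4.5/9/9 and requiring omnibus rejection first, gives:

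| Reading | Critical value | CI for 4.5 | Probability per dose |
|---|---|---|---|
| Two comparisons with sham | 1.940 | (1.05, 7.95) | 0.706 |
| Three pairwise comparisons | 2.078 | (0.81, 8.19) | 0.671 |

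**The case against.** The strongest reply is that the protocol says openly that the SE applies in each arm. Section 9.4.2 also models the change in each arm and takes the fitted day-15 estimate as the primary outcome. Arm-level means and SDs are useful inputs to later planning, the printed interval is offered only as an example, and the between-arm question is covered by the 83% power. No decision rule uses the one-arm interval, so the false-exclusion rates in step 5 belong to a rule that nobody will apply.

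Much of this stands. The arithmetic is right, its basis is disclosed, and under sections 9.1 and 9.4.2 no dose would be declared effective on the one-arm comparison. What remains is that section 9.2 calls the one-arm quantity a treatment effect and sets it against a null. Disclosing the basis does not make that comparison one of stimulation against sham. Omnibus power also does not state how precisely a dose-versus-sham difference will be estimated.

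Three further points limit the figures:
- The 31 per arm precedes inflation. If all 43 per arm were evaluable, the SE of the difference would be 7 × √(2/43) = 1.51 and the 90% CI about (2.0, 7.0), ignoring any dilution from incomplete treatment.
- Covariate adjustment and repeated measures could narrow the interval, but section 9.2 says robust estimates of these quantities are not available.
- Figure 9, on the trade-off between precision and sample size, could not be seen. The statement that no between-arm precision is given applies to the visible text only.

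**Conclusion.** The concern holds and is confined to the precision statement in section 9.2. With 31 evaluable subjects per arm and SD 7, active minus sham has SE 1.78, where the text prints 1.3 for a treatment effect in each arm. The 90% half-width is 2.9 points, not 2.1. The unadjusted interval of about 4.5 (1.6, 7.4) excludes 0, but its lower limit is well below the 4.25 to 7.25 range that section 9.2 cites as clinically important. The probability that the interval excludes its null falls from about 97% for the one-arm criterion to about 81% for the difference. That 81% is before the correction in section 9.4.2.

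The sample size, alpha, hypotheses, analysis model and 83% power all stand. The correction is worth making because precision is the first justification given for 31 per arm, and the text offers it as adequate for Phase III planning.

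**What to change.** Change the text of section 9.2 in two places.

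1. In the sentence that gives 31 subjects per arm, describe the quantity with SE 1.3 as the mean change from baseline within each arm, not as a treatment effect.
2. Replace the sentence about excluding 4.5 with wording such as:

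> With 31 evaluable subjects per arm and SD 7, the mean change within an active arm has SE 1.3; for a mean of 9.0 its 90% CI would be (6.9, 11.1). Each active-minus-sham difference has SE 1.78; for a difference of 4.5 its unadjusted 90% CI would be about (1.6, 7.4). That unadjusted interval excludes 0 with about 81% probability when the true difference is 4.5.

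The sponsor should confirm that its statement on adequacy for Phase III planning still holds against the between-arm interval. A per-dose probability after multiplicity correction should be added only if the number of comparisons is stated with it.

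The cost is a less favourable stated precision. The 129 subjects, alpha, power, hypotheses and model do not change.

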9.3 POPULATIONS FOR ANALYSES

- Intent-to-treat (ITT) population

All analyses will be conducted under the ITT principle. That is, the evaluable sample includes all randomized subjects, regardless of whether or not the subjects completed the study protocol; where subjects are classified according to the intervention assignment, they are randomized into.

- Per-protocol (PP) population

Sensitivity of the primary findings will be assessed using a per-protocol sample defined as all subjects who (a) complete at least 8 out of 10 sessions of the intervention; (b) complete the FM-UE scale with all three post-intervention visits; (c) do not experience a recurrent clinical stroke or other pre-specified illness known to impact upper extremity motor functioning during the study period (i.e., Bone fracture in the affected arm, newly diagnosed neuromuscular disease, cervical spine injury.); and (d) do not receive any other forms of rehabilitation therapy after 2 weeks of intervention. The intent of this analysis sample is to assess the maximum possible treatment effect achievable with tDCS at a dose of either 2 mA or 4 mA. It is anticipated that <50% of subjects will receive additional forms of rehabilitation therapy after the 14 day intervention (subjects enrolled in the subacute phase are the ones who have likely received additional rehabilitation therapy), however, if this percentage exceeds 50% the PP sample will exclude criteria (d).

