6 STUDY INTERVENTION

6.1 STUDY INTERVENTION(S) ADMINISTRATION

6.1.1 STUDY INTERVENTION DESCRIPTION

Transcranial Direct Current Stimulation (tDCS):

tDCS will be delivered to the study subjects through two electrodes ($5 \times 7 = 35 \text{ cm}^2$) via a direct current delivery device. In the bihemispheric montage, the anodal electrode will be placed over the ipsi-lesional and the cathodal electrode over the contra-lesional motor cortex (C3 and C4 using the international 10-20 EEG electrode systems). Electrode pads will be disposed after each week or 5 sessions. Pads will not be shared across subjects. Stimulation will last for 30 minutes (± 6) minutes for each session. Subject will receive either sham, 2 mA or 4 mA. Records of current will be checked and kept separately without unbinding the sites.

mCIMT:

The mCIMT protocol in this study is adapted from a protocol published in the EXCITE and VECTOR trials^{14, 19}. The premise of the strategy is that repetitive object grasping and manipulation practice reduces the effects of “learned non-use.” mCIMT will be delivered 120 minutes (\pm 24) minutes a day (with the first 30 minutes (\pm 6) minutes simultaneously with tDCS stimulation) for 10 sessions over 2 weeks with the unaffected arm in a constraining mitt for at least 6 hours/day during waking hours. Subjects will not be allowed to use the constrained hand within the task effort. The tasks attempted during the therapy session will be menu driven. Activities will be selected from a task menu, and an activity log kept demonstrating what tasks have been attempted. Each activity will be carried out for 15-30 minutes and activities selected should be challenging yet feasible for the subject, contextually appropriate (i.e., with regards to interests) and challenge movements that need improvement.

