6.3 MEASURES TO MINIMIZE BIAS: RANDOMIZATION AND BLINDING

On the randomization day, a study coordinator or a team member will log into WebDCU™ to randomize subjects who have been consented and found eligible. Briefly, at the beginning of each intervention session, the coordinator will complete tDCS Treatment Activation Code Request to obtain a new tDCS treatment activation code daily. Each day, the coordinator will need to enter the new code into the tDCS machine which will translate the code to the appropriate stimulation voltage using a pre-loaded script (**Fig 8, right**). The treating therapist is only to conduct mCIMT on the study subject, another study team member should conduct concurrent tDCS stimulation session to avoid potential bias.

Subjects will be allocated equally among the three treatment arms using a covariate adaptive randomization algorithm which controls for serious imbalances in covariates considered to have an impact

[figure not shown]

Fig 8. Schematic of interface between tDCS control, dual-channel tDCS delivery system, and WebDCU™ interface.

on outcome; specifically, study site, time from stroke, and baseline motor impairment measured using FM-UE scale. At the time of randomization, serious imbalances in these covariates will be accounted for using a minimal sufficient balance approach¹⁰⁵. That is, at the time of randomization, an overall treatment imbalance and imbalance in each of the covariates is assessed. If no imbalances exceed the tolerated threshold, the subject is randomized according to the specified allocation ratio (1:1:1). If an unacceptable level of imbalance exists, the algorithm will determine whether the current allocation ratio improves or exacerbates the current imbalance and adjust the ratio accordingly. The detailed randomization scheme and source codes will be provided in the Randomization Plan document.

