9.4.4 SAFETY ANALYSES

Safety: Analysis Method

IMSM and Data and Safety Monitoring Board (DSMB) will receive periodic safety reports of all reportable adverse events including serious adverse events (SAEs) if there are any. All clinical safety endpoints and SAEs will be summarized by AE code (as provided on the AE CRF) regarding the frequency of the event, the number of subjects having the event, severity, and relatedness to the study treatment. Clinically important adverse events include:

- Severe headache
- Second-degree skin burn
- Clinical seizure
- Neurological deterioration (\geq 4-point increase in NIHSS)

The proportion of subjects experiencing each of these events will be provided in the closed report by intervention arm with two-sided 95% CIs and unadjusted relative risks. Based on the Phase I dose-escalation study, no subjects experienced any of the clinically important adverse events. Fisher's exact tests will be used to assess intervention group differences in the rates of clinically important adverse events.

Tolerability: Analysis Method

Tolerability will primarily be measured through the use of the Visual-Analog scale (VAS), a 10-point scale ranging from 0 (No Discomfort) to 10 (Extreme Discomfort). For the primary analysis, any subject who requests to be withdrawn from the study due to procedure related issues will be imputed as a 10 on the Visual-Analog Scale. Differences in tolerability will be assessed using a Kruskal-Wallis test at a 10% type-I error rate.

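### Section 9.3 places safety under ITT too, so if any subject receives a current other than the one assigned, an adverse event can be counted under the wrong dose

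*Combined protocol and SAP*

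**What the plan says.** Section 9.3 opens its list of populations with the rule that "All analyses will be conducted under the ITT principle". The evaluable sample is all randomized subjects, "where subjects are classified according to the intervention assignment, they are randomized into". The only other population is per-protocol, and its use is narrow: "Sensitivity of the primary findings will be assessed using a per-protocol sample".

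Section 9.4.4 covers four clinically important adverse events: severe headache, second-degree skin burn, clinical seizure and neurological deterioration. For these, "The proportion of subjects experiencing each of these events will be provided in the closed report by intervention arm with two-sided 95% CIs", and Fisher's "exact tests will be used to assess intervention group differences in the rates of clinically important adverse events". It names no analysis population and no significance level for that test.

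Section 6.3 describes how the current is set. A new activation code is obtained at every session. "Each day, the coordinator will need to enter the new code into the tDCS machine", and a pre-loaded script converts the code into the stimulation setting. Section 6.1.1 adds: "Records of current will be checked and kept separately without unbinding the sites". No analysis in the protocol uses those records.

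The synopsis (1.1, Secondary Objectives) treats the intervention as safe if adverse event rates do not differ significantly.

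**The concern.** Current is the variable under study, and whether 4 mA keeps a similar safety and tolerability profile to 2 mA is an explicit question in 9.4.1. Read literally, 9.3 and 9.4.4 together count a burn that occurred at 4 mA in a subject assigned to sham as a sham event.

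For efficacy, counting by assignment is the cautious choice, because mixing the arms makes a benefit harder to claim. For safety the direction reverses. Mixing the arms makes a difference harder to find, and here finding no difference is the success criterion. Section 9.4.4 notes that Phase I saw none of these events, so counts are likely to be small and each event carries weight.

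**Working it through.** **1. Which population governs the safety tables.** The rule in 9.3 covers all analyses and makes no exception. The per-protocol set serves the primary efficacy finding only. Section 9.4.4 speaks of intervention arms and groups and names no set, so the 9.3 rule applies and arms mean arms as randomized. This is a stated rule rather than a gap in detail.

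**2. Arm size.** Section 9.2 gives 31 per arm, inflated by 1/(1 − 0.08)² and then by 1.15: 31 / 0.8464 = 36.63, and 36.63 × 1.15 = 42.12, rounded up to 43. The plan's 43 per group reproduces and is the denominator below.

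**3. Direction of the bias.** Let p0 and p4 be the true event rates on sham and at 4 mA, and let m be the share of subjects given the other setting throughout.
- One-way (a share m of the 4 mA arm receives sham): the assigned-arm rate at 4 mA is (1 − m)p4 + m·p0, so the risk difference is (1 − m)(p4 − p0).
- Mutual (the same share of the sham arm also receives 4 mA): the risk difference is (1 − 2m)(p4 − p0).

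For any m between 0 and 0.5, both are smaller than the true difference. At m = 0 they equal it.

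**4. One misplaced subject.** Two-sided Fisher test, 4 mA against sham; the counts are hypothetical.

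| Classification | 4 mA | Sham | p |
|---|---|---|---|
| By delivered setting | 6/44 | 0/42 | 0.026 |
| By assignment, one of the six subjects assigned to sham | 5/43 | 1/43 | 0.20 |

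The first result is significant at 5% and the second is not significant even at 10%.

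**5. Power when misdelivery affects whole subjects.** Assumptions not in the documents: alpha 0.05 two-sided, a pairwise test of 4 mA against sham, 43 per arm, a true sham rate of 0%, and m of 5% or 10% (about 2 or 4 of 43 subjects). The last two columns give one-way misdelivery, with mutual misdelivery in parentheses.

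| True 4 mA rate | By delivered setting (m = 0) | m = 5% | m = 10% |
|---|---|---|---|
| 10% | 26% | 22% (19%) | 19% (13%) |
| 15% | 64% | 59% (49%) | 53% (37%) |
| 20% | 88% | 85% (75%) | 81% (60%) |

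**6. What cannot be calculated.** The documents give no value for m. They also do not say what the device does when a code is entered wrongly. Steps 4 and 5 therefore show sensitivity, not an expected effect.

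**The case against.** The strongest reply is that misdelivery may hardly occur. Codes are generated centrally, renewed each session and translated by a script, and 6.1.1 says the current records are checked. That stands: with no misdelivery, both classifications give the same table.

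Three stronger readings are tempting and are not supported.

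- A reader might take the 129 × 10 = 1,290 planned code entries, apply an error rate and count sessions run at the wrong current. Nothing in the documents gives such a rate or shows that a wrong entry starts stimulation at another arm's setting. One wrong session in ten also does not make a wholly misclassified subject, so session counts cannot be carried into the subject-level figures above.
- A reader might infer that never-stimulated subjects dilute the dose arms. The Schedule of Activities (1.3) places randomization at the first treatment session, after eligibility is confirmed, so such subjects should be rare. The 8% expected in 9.2 to complete fewer than ten sessions are under-exposed, not given another arm's current, and regrouping would not move them.
- A reader might conclude that the plan does hide a dose-related harm. It could, but a lone misplaced event leaves the planned test unchanged: 1/43 against 0/43 gives p = 1.0 in either direction. What moves is the exact 95% upper limit for the arm, which is 12.3% for 1/43 and 8.2% for 0/43.

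Independent medical review of serious events and the DSMB's by-arm reports (8.2.4, 8.2.6, 10.1.6) are real safeguards. However, relatedness review does not reassign an event to another arm, and the closed report is the same by-arm tabulation that 9.4.4 describes.

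Finally, 9.4 defers details to the SAP, and no separate SAP text is in the document supplied. A safety set may be defined there. If so, it would conflict with the blanket rule in 9.3, and that wording would still need correcting.

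**Conclusion.** The point holds as a modest one. The protocol explicitly places safety under assignment-based classification in a trial where dose is the exposure. Any departure of delivered from assigned current would bias toward the protocol's own criterion for safety. The direction follows from the algebra whenever the true event rate differs between settings.

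The size is unknown and may be zero. The illustrative power losses (for example 64% to 59% one-way, or 49% mutual, at m = 5% and a true 4 mA rate of 15%) rest entirely on assumed misdelivery shares and event rates. The case for change is that the needed records already exist, the remedy is standard and cheap, and settling the rule before unblinding avoids a later choice that could turn on a single event.

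**What to change.** - **Section 9.3:** limit the ITT statement to efficacy analyses.
- **Section 9.3:** add a safety set of all subjects who received at least one tDCS session, sham included. Classify by the arm setting actually delivered (sham, 2 mA or 4 mA) according to the current records in 6.1.1. Use the setting rather than a highest-current rule: one stray session would otherwise move all of a subject's events, and the protocol does not give the current delivered during sham.
- **Mixed exposure:** state a rule. For example, classify by the setting delivered in most sessions, list every subject with any off-assignment session, and report each of their events with the setting delivered at or before onset.
- **Section 9.4.4:** name this set for the safety and tolerability analyses, and keep the as-randomized table as supporting.
- **SAP:** align its wording with the protocol.

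The cost is a wording change, one extra table and a listing, prepared by the unblinded statistician so that site blinding is preserved. No new data are needed, and neither the 43 per group nor the stated 83% power changes.
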